#### Baseline definition

The baseline for plasma AGT will be define as the average of all values on prior to the first dose of Study Drug. The baseline for all other assessments will be defined as the last non-missing measurement prior to the first dose.

#### Analytical visits

Data will be summarized using the visit labels provided in the data. Multiple results with the same visit label will be averaged. Results with visit labels as "Unscheduled" will not be included in the by-visit summary tables and figures except for determining baseline and the analysis of confirmed ALT/AST category (see section 3.7.3) but will be presented in data listings.

#### 3.2.2 Subject Population Analyzed

The following analysis populations are defined for this study:

- Full Analysis Set (FAS): All randomized subjects who have received at least 1 injection of Study Drug (ISIS 757456 or Placebo) and who have at least 1 post-Baseline efficacy or exploratory measurements.
- Per Protocol Set (PPS): All FAS subjects who received at least 7 of the 9 doses of Study Drug, did not alter antihypertensive medications during the Treatment Period and prior to Study Day 57, and have no significant protocol deviations that would be expected to affect efficacy or exploratory assessments.
- Safety Set: All subjects who are randomized and receive at least 1 dose of Study Drug.
- Pharmacokinetics (PK) Set: All subjects who are randomized and receive at least 1 dose of ISIS 757456 and have at least 1 evaluable PK sample.

In addition to the above analysis sets, it is recognized that some data displays will be provided for "All Screened", "Screening Failures" and "All Randomized" subjects but no data analysis will be executed in these populations.

### **3.2.3 Handling of Missing Data**

Missing values will not be imputed. Patients with missing data for a scheduled assessment time point were excluded from the summary for that time point.

### **3.2.4 Demographic and Baseline Characteristics**

Demographic and Baseline characteristics (e.g., age, gender, ethnicity, race, cardiovascular disease (CVD) risk factors, weight, height, BMI) will be summarized using descriptive statistics by treatment group.

BMI will be computed using the formula:  $BMI = (\text{weight in kilograms}) / [\text{screening height in cm} / 100]^2$

Subject randomization and disposition will be summarized by treatment group. All subjects enrolled will be included in the summary.

Protocol deviations will be listed.

[figure not shown]
## **3.3 Primary Analysis**

### **3.3.1 Primary Efficacy Analysis**

The primary analysis will be the comparison of percent change from Baseline to Study Day 57 (Study Week 9) in plasma AGT between ISIS 757456 80 mg group and placebo group in PPS. The data will be analyzed using analysis of variance (ANOVA) with treatment and randomization stratification factor (screening ACE/ARB dose status) as independent variables. The normality assumption for the ANOVA model will be assessed by the Shapiro-Wilks test on the residuals. In the case data departs substantially from normality, the nonparametric Van Elteren test (van Elteren, 1960) will be employed instead. Additional analysis summary based on the FAS will also be provided.

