### **1.2. Study Endpoints**

#### **1.2.1. Primary Endpoint**

Percent change in plasma AGT from Baseline to Study Day 57 (Study Week 9) compared to placebo

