### 5.1. Inclusion Criteria

1. Must have given written informed consent (signed and dated) and any authorizations required by local law and be able to comply with all study requirements
2. Males or females aged 18–75 inclusive and weighing  $\geq 50$  kg at the time of informed consent
3. Satisfy the following:
  - a. Females: must be non-pregnant and non-lactating, and either:
    - i. surgically sterile (e.g., tubal occlusion, hysterectomy, bilateral salpingectomy, bilateral oophorectomy) or,
    - ii. post-menopausal (defined as 12 months of spontaneous amenorrhea in females  $> 55$  years of age or, in females  $\leq 55$  years, 12 months of spontaneous amenorrhea without an alternative medical cause and follicle stimulating hormone (FSH) levels in the postmenopausal range for the laboratory involved)
  - b. Males: Surgically sterile (i.e., bilateral orchidectomy) or abstinent\*, if engaged in sexual relations with a woman of child-bearing potential (WOCBP), the subject or subject's non-pregnant female partner must be using a highly effective contraceptive method from the time of signing the informed consent form until at least 13 weeks after the last dose of Study Drug (ISIS 757456 or placebo)

\* True abstinence (i.e., refraining from heterosexual intercourse throughout the duration of study participation) is only acceptable. Periodic abstinence (e.g., calendar, ovulation, symptothermal, post-ovulation methods), declaration of abstinence for the duration of a trial and withdrawal are not acceptable methods of contraception

4.  $BMI \leq 35.0 \text{ kg/m}^2$
5. Brachial circumference  $\geq 22$  and  $\leq 37$  cm (8.7 and 14.6 inches)
6. Subject must have been diagnosed with essential HTN for a minimum of 3 months prior to screening
7. At Screening, the subject must have a plasma AGT concentration  $\geq 20 \text{ } \mu\text{g/mL}$ . Up to 1 additional repeat test may be allowed in order to qualify with consultation of the Sponsor Medical Monitor
8. At Screening, the subject must have been on a stable regimen of 2 to 3 antihypertensive medications for at least 1 month prior to screening and will be required to maintain this regimen throughout the Study, using either an angiotensin-converting enzyme inhibitor (ACEi) or an angiotensin II receptor blocker (ARB), as well as 1 or 2 additional antihypertensive medications in the following categories:
  - a. beta blocker
    - i. acebutolol
    - ii. atenolol
    - iii. betaxolol
    - iv. bisoprolol

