## 10. STATISTICAL CONSIDERATIONS

### 10.1. Stratification, Subsets, and Covariates

Subjects will be stratified based on either low Screening ACE/ARB dose or high Screening ACE/ARB dose. The **total** dose of the ACE or ARB taken per day is to be calculated based off their stable regimen of antihypertensive medications at Screening. Please refer to [Appendix E](#) for stratification criteria.

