### **10.6.3. Efficacy Analysis**

The primary analysis will be the comparison of percent change from Baseline to Study Day 57 (Study Week 9) in plasma AGT between ISIS 757456 80 mg group and placebo group in the Per Protocol Set. The data will be analyzed using analysis of variance (ANOVA) with treatment and randomization stratification factor (low ACE/ARB dose regimen vs. high ACE/ARB dose regimen) as independent variables. In the case data departs substantially from normality, the nonparametric van Elteren test will be employed instead.

The secondary efficacy analyses will be performed in a similar way to the primary analysis, which include:

- Comparison of change and percent change from Baseline to each schedule post-Baseline visit in AGT between ISIS 757456 80 mg group and placebo group in Per Protocol Set (PPS) and FAS
- Comparison of change from Baseline to each schedule post-Baseline visit in in-clinic SBP and DBP between ISIS 757456 80 mg group and placebo group in PPS and FAS

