### 3.2 General Overview of Analyses

#### 3.2.1 Statistical Methods

Descriptive summary statistics including number of subjects, mean, median, standard deviation, standard error of mean, 25th percentile, 75th percentile, minimum, and maximum for continuous variables, and counts and percentages for categorical variables will be provided to summarize most data. Additional subject listings included case report form (CRF) data and derived outcomes from the data may be presented.

All statistical tests will be conducted using 2-sided tests with 5% Type I error rate unless otherwise stated. P-values will also be provided as an indicator to summarize how incompatibility between ISIS757456 and placebo cohort based on the statistical model. Unless specified, the stratification factor (screening ACE/ARB dose status) and treatment received are included in the model as independent variables.

PK parameters will be summarized using include number of subjects, mean, standard deviation, coefficient of variation (CV), geometric mean, median, minimum, and maximum.

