### 3.4 Secondary Efficacy Analyses

The secondary efficacy analyses will be performed in a similar way to the primary analysis, which include:

- Comparison of change from Baseline to each scheduled post-Baseline visit in SBP between ISIS 757456 80 mg group and placebo group in PPS and FAS
- Comparison of change and percent change from Baseline to each scheduled post-Baseline visit in AGT between ISIS 757456 80 mg group and placebo group in PPS and FAS.

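### The primary ANOVA of percent change in plasma AGT omits baseline AGT; at about 20 versus 10 subjects, chance imbalance can enter the estimate and precision may be lost

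*Combined protocol and SAP*

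**What the plan says.** The primary endpoint in protocol 1.2.1 is: "Percent change in plasma AGT from Baseline to Study Day 57 (Study Week 9) compared to placebo". SAP 3.3.1 restricts its analysis to the Per Protocol Set and gives this model: "The data will be analyzed using analysis of variance (ANOVA) with treatment and randomization stratification factor (screening ACE/ARB dose status) as independent variables". Protocol 10.6.3 has the same model: "The data will be analyzed using analysis of variance (ANOVA) with treatment and randomization stratification factor". SAP 3.2.1 makes these terms the default for other models: "the stratification factor (screening ACE/ARB dose status) and treatment received are included in the model as independent variables". If residuals are clearly non-normal, the van Elteren test replaces the ANOVA; it does not use baseline AGT either.

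SAP 3.4 applies a similar analysis to the secondary AGT endpoints: "Comparison of change and percent change from Baseline to each scheduled post-Baseline visit in AGT". Appendix A of the protocol schedules 14 post-baseline AGT visits.

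Baseline AGT is already defined in SAP 3.2.1: "The baseline for plasma AGT will be define as the average of all values on prior to the first dose of Study Drug". Appendix A schedules AGT at Screening and pre-dose on Day 1. A Screening value is an entry requirement (protocol 5.1): "At Screening, the subject must have a plasma AGT concentration" of at least 20 µg/mL, with one repeat possible. The only stratification factor is in protocol 10.1: "Subjects will be stratified based on either low Screening ACE/ARB dose or high Screening ACE/ARB dose".

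**The concern.** Baseline AGT is available for every eligible subject but is used only as the denominator of the percent change, or as the value subtracted for absolute change. Balance on it is left to chance in a trial of about 30 subjects randomised 2:1.

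Dividing by baseline does not fully remove dependence on baseline. Where the baseline value contains measurement error, a subject whose baseline is high by chance shows a larger apparent fall, and one whose baseline is low by chance a smaller fall. Averaging two pre-dose values weakens this but does not abolish it. For absolute change the dependence is direct, because the same percent reduction is a larger fall in µg/mL from a higher baseline.

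If the arms differ at baseline by chance, part of that difference can enter the primary estimate and the AGT visit estimates, and the intervals may be wider than the collected data allow. If the imbalance is noticed only after unblinding, any adjustment is post hoc.

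**Working it through.** The visible text gives no power, effect size, SD or correlation, so there is no planned figure to reproduce. Everything below that uses a correlation or an SD rests on an assumption.

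**Inputs from the documents.** About 30 subjects (protocol 3.3); 2:1 allocation (SAP 2.2), so about 20 versus 10; two-sided 5% tests (SAP 3.2.1). The planned ANOVA fits an intercept, treatment and stratum, so residual df = 30 - 3 = 27. Adding one covariate gives 26.

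**Step 1: chance imbalance.** The SE of the baseline difference, in baseline SDs, is sqrt(1/20 + 1/10) = 0.387, so the 95% range is ±1.96 × 0.387 = ±0.76 SD. The probability of a difference above 0.5 SD in either direction is 2 × P(Z > 0.5/0.387) = 0.20. If the Per Protocol Set fell to 16 versus 8, the SE would be 0.433 and the probability 0.25.

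**Step 2: what carries over.** Let rho be the size of the within-arm correlation between baseline AGT and the outcome. A one-SE imbalance shifts the unadjusted estimate by rho × 0.387 outcome SD: 0.04 at rho 0.1, 0.12 at 0.3 and 0.19 at 0.5.

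**Step 3: variance and power.** The expected ANCOVA/ANOVA variance ratio is (1 - rho²) × (1 + 1/(df - 2)) = (1 - rho²) × 1.04. The factor 1.04 is the cost of estimating the covariate slope. Break-even is at rho = sqrt(1 - 1/1.04) = 0.196, or 0.22 at 16 versus 8.

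For power, assume the planned ANOVA has 80%. With 27 df this needs a standardised effect of 1.126, that is a noncentrality of 1.126/0.387 = 2.91. The adjusted analysis has noncentrality 2.91/sqrt(variance ratio) on 26 df.

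| Assumed rho | Variance ratio | SE ratio | Power, ANCOVA |
|---|---|---|---|
| 0 | 1.04 | 1.02 | 78% |
| 0.2 | 1.00 | 1.00 | 80% |
| 0.3 | 0.95 | 0.97 | 82% |
| 0.4 | 0.87 | 0.94 | 85% |
| 0.5 | 0.78 | 0.88 | 89% |

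**Step 4: which rho is plausible?** This was simulated with 20 versus 10 subjects, log-normal AGT, Screening AGT of at least 20 µg/mL, and baseline as the mean of two pre-dose values. Between-subject log-scale SDs of about 0.15 to 0.3 and within-subject SDs of about 0.05 to 0.3 were assumed.

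- Percent change: ANCOVA/ANOVA variance ratio about 0.86 to 1.06. With within-subject SD of 0.05 to 0.10 the ratio was close to 1. Ratios near 0.86 to 0.89 needed within-subject SD of 0.2 to 0.3 together with between-subject SD of only 0.15.
- Absolute change, true reduction 50%: about 0.72 to 0.98, with the least gain where baseline is nearly error-free.
- Mean estimates from ANOVA and ANCOVA agreed within about 0.2 percentage points for percent change, so neither is systematically shifted relative to the other.

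**The case against.** Several points on the other side stand. Percent change already scales each subject to their own baseline, and the averaged baseline reduces measurement error further, so only residual dependence is at issue. Below |rho| of about 0.2, adjustment gains nothing or costs a little. No correlation or SD is visible, so a gain for the primary endpoint cannot be established from the documents. If the AGT effect is very large, power is near 100% with either model.

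A reader might infer that leaving out baseline biases the primary result, or that the entry threshold with its permitted repeat does so through regression to the mean. The documents do not support this. Treatment is randomised, so the unadjusted estimate is unbiased on average, and the threshold is applied before randomisation and affects both arms alike.

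Two further points have less force. SAP 3.1 calls the outcomes descriptive and protocol 3.3 justifies the sample size by safety and tolerability, but SAP 3.2.1 still plans two-sided 5% tests and SAP 3.3.1 a formal primary comparison. Parts of the SAP around Section 3.4 are redacted and could hold a baseline-adjusted supportive analysis. That cannot be excluded, but the primary model sentence is complete as it stands.

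**Conclusion.** The point holds as one of efficiency and of protection against chance imbalance, not of validity. The omission is plain in both documents, and an imbalance above 0.5 SD has about a one-in-five chance at 20 versus 10.

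It would go too far to say that precision is lost in the primary analysis. It may be lost, and under some of the assumed settings adjustment makes the variance slightly larger. The case is stronger for the secondary analysis of absolute AGT change, where every setting in the quoted range favoured adjustment under a true 50% reduction. The power figures rest on an assumed 80% for the planned ANOVA; with a very large AGT effect, what remains is interval width and protection against imbalance. This is an inexpensive improvement rather than a defect that threatens the trial's conclusion.

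**What to change.** In SAP 3.3.1 and protocol 10.6.3, specify an ANCOVA with treatment, ACE/ARB stratum and log baseline AGT, using the pre-dose average already defined in SAP 3.2.1. Use the same model for the AGT change and percent-change comparisons in SAP 3.4. Keep the unadjusted ANOVA as a sensitivity analysis.

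Also state what happens if the normality check fails, since a switch to van Elteren alone would drop the covariate again. The baseline-adjusted estimate should still be reported alongside that test, for example from an ANCOVA on log AGT or a stratified rank test on baseline-adjusted residuals.

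No new data are needed. The cost is one residual degree of freedom (27 to 26) and a variance increase of a few percent if baseline is unrelated to percent change. Settling this before unblinding avoids a post hoc adjustment that SAP Section 1 would require to be documented in the study report as a deviation.

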### 3.3.2 Planned Interim Analysis

[figure not shown]
An interim analysis may be conducted after at least 50% of the subjects have been enrolled. All study primary and secondary efficacy endpoints will be summarized descriptively.

### 3.4 Secondary Efficacy Analyses

The secondary efficacy analyses will be performed in a similar way to the primary analysis, which include:

- Comparison of change from Baseline to each scheduled post-Baseline visit in SBP between ISIS 757456 80 mg group and placebo group in PPS and FAS
- Comparison of change and percent change from Baseline to each scheduled post-Baseline visit in AGT between ISIS 757456 80 mg group and placebo group in PPS and FAS.

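### SBP change is modelled without baseline SBP, so part of any chance baseline imbalance between about 20 and 10 subjects carries into all 14 visit estimates (minor, optional change)

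*Combined protocol and SAP*

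**What the plan says.** SAP 3.4 lists a "Comparison of change from Baseline to each scheduled post-Baseline visit in SBP between ISIS 757456 80 mg group and placebo group", in both the per-protocol and full analysis sets. On method it says: "The secondary efficacy analyses will be performed in a similar way to the primary analysis". For the primary analysis, SAP 3.3.1 says: "The data will be analyzed using analysis of variance (ANOVA) with treatment and randomization stratification factor (screening ACE/ARB dose status) as independent variables". SAP 3.2.1 makes those two terms the default: "Unless specified, the stratification factor (screening ACE/ARB dose status) and treatment received are included in the model as independent variables". Protocol 10.6.3 has the same two-term model and includes diastolic pressure: "Comparison of change from Baseline to each schedule post-Baseline visit in in-clinic SBP and DBP". SAP 3.4 does not list DBP. Protocol 10.1 has covariates in its heading but names only the ACE/ARB stratum.

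For SBP, the SAP's baseline rule is: "The baseline for all other assessments will be defined as the last non-missing measurement prior to the first dose". So a single pre-dose value per subject is subtracted at every visit. Inclusion criterion 9 (protocol 5.1) requires mean seated SBP above 140 and no higher than 170 mmHg, both at Screening and before dosing on Day 1. It permits up to two further tests each time. Under Analytical visits, the SAP adds: "Multiple results with the same visit label will be averaged".

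On inference, SAP 3.2.1 states: "All statistical tests will be conducted using 2-sided tests with 5% Type I error rate unless otherwise stated". SAP 3.1 calls the outcomes descriptive. Some SAP entries near 3.3.2 and 3.4 are redacted and could hold an adjusted analysis; nothing readable provides one.

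**The concern.** Subtracting baseline does not remove a chance baseline difference unless follow-up SBP rises one-for-one with baseline SBP. It will not: a single pre-dose value contains visit-to-visit noise, and subjects enter only if they are high on two occasions, so some regression to the mean is expected. Change therefore depends negatively on baseline, and the arm that happens to start higher shows the larger fall with or without a drug effect.

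SBP is the trial's secondary objective. Readers will see its change plotted or tabulated at 14 visits, and agreement across visits invites the reading that the result is corroborated. Part of that agreement can come from one baseline difference repeated 14 times.

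**Working it through.** **Figures in the plan.** The readable text gives no SBP SD, effect size or power, so there is no stated figure to reproduce. Two counts can be confirmed:
- About 30 subjects at 2:1 is 20 versus 10.
- Appendix A has vital signs on Days 3, 8, 15, 22, 29, 36, 43 and 50 (8 visits) and Days 57, 64, 78, 92, 120 and 141 (6 visits), which makes 14.

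**Size of a chance imbalance.** SE of the baseline difference = SD_b × √(1/20 + 1/10) = 0.387 × SD_b. An imbalance above 1 SE occurs in about 32% of randomizations, as for any normal variable.

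**Carry-over.** Let b be the slope of follow-up SBP on baseline SBP, and D the baseline difference (active minus placebo). Given D, the unadjusted estimate is centred on the true effect minus (1 − b) × D. For example, with SD_b = 8 and b = 0.5, the SE is 0.387 × 8 = 3.10 mmHg and the shift is 0.5 × 3.10 = 1.55 mmHg. Assumed ranges give:

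| SD_b (mmHg) | 1 SE of D | Shift, b = 0.3 | b = 0.5 | b = 0.7 |
|---|---|---|---|---|
| 6 | 2.32 | 1.63 | 1.16 | 0.70 |
| 8 | 3.10 | 2.17 | 1.55 | 0.93 |
| 10 | 3.87 | 2.71 | 1.94 | 1.16 |

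**Simulation with the entry window.** All of these inputs are assumptions: true mean 145, 150 or 155 mmHg; between-subject SD 10 or 12; visit SD 6, 9 or 12 (18 scenarios). The entry window was applied at Screening and Day 1, with two strata of 15, 20 versus 10, no true effect, and 40,000 trials per scenario. Baseline was formed in three ways, because the criterion allows repeat tests:

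| How baseline is formed | Slope of change on baseline | Shift for 1-SE imbalance (mmHg) | Variance ratio ANCOVA/ANOVA (median) |
|---|---|---|---|
| One test per time point | −0.67 to −0.32 | 0.9-2.1 | 0.896-0.953 (0.923) |
| Up to 2 repeats, first qualifying average kept | −0.59 to −0.15 | 0.5-1.8 | 0.939-1.016 (0.978) |
| Up to 2 repeats, all same-visit results averaged | −0.54 to −0.21 | 0.7-2.1 | 0.903-0.986 (0.943) |

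One SE of imbalance was 2.7-3.1 mmHg in the first row and 3.1-4.1 mmHg in the third. The shift is 0.15-0.37 of the unadjusted SE (3.1-5.9 mmHg). After adjustment the carry-over slope was −0.02 to 0.01.

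**Sensitivity.**
- If same-day repeats share half the visit variance, the shift is 0.7-1.8 mmHg in the second row and 0.9-2.4 mmHg in the third.
- With a per-protocol set assumed to be 16 versus 8, the shift is 0.5-2.3 mmHg, and the variance runs from a 9% cut to a 3% loss.

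**Error rates at one visit.**

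| Trials considered | Unadjusted | Adjusted |
|---|---|---|
| All | 4.8-5.3% | 4.8-5.3% |
| Imbalance > 1 SE (32%) | 5.3-7.2% | 4.6-5.5% |
| Imbalance > 1.96 SE (5%) | 6.0-13.3% | 3.9-6.2% |

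**Across 14 visits** (8,000 trials per scenario). Given an imbalance above 1 SE and no true effect, 59-74% of visit estimates lean the way the imbalance favours, against 49-51% after adjustment. Mean correlation between visit estimates is 0.34-0.47 unadjusted and 0.25-0.46 adjusted. Adjustment removes 0-37% of the cross-visit covariance.

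**Price of the covariate.** If change were unrelated to baseline, estimating the slope would inflate the variance by about 1/(27 − 2) = 1/25 = 4% at 30 subjects, or 1/(21 − 2) = 1/19 = 5% at 24.

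**The case against.** The strongest reply is that nothing here is wrong. ANOVA on change is valid, its type I error is nominal, and the estimate is unbiased over randomizations. The choice between it and ANCOVA is then one of precision, and the gain is small and uncertain. If the first qualifying average is kept, the median variance ratio is 0.978 and the upper end of the range is a 2% loss. Every SD is assumed. The 32% figure holds for any normal variable. The 59-74% figure is conditional on that third of trials; over all randomizations a shift of 0.15-0.37 SE implies sign agreement of only about 55-62% (0.5 + arcsin(r)/π with r = 0.15 to 0.37). Most of the correlation between visits is subject-level variation that the covariate leaves in place. Visits that switch to the van Elteren test stay unadjusted. Protocol 12.1 attaches approvals and notifications to an amendment, and a redacted section may already contain the adjusted analysis.

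All of that stands as a limit on importance, and it keeps the point at the lowest grade. It does not remove the point. Once the trial is run there is one realised imbalance, and the unadjusted profile carries part of it. Descriptive estimates are read for their size, and the plan still attaches tests to them. Naming the covariate beforehand also avoids deciding on adjustment after an imbalance has been seen. The amendment burden is no bar, because the default in SAP 3.2.1 already leaves room to specify a different model.

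**Conclusion.** The point holds and is minor. On the readable text, SBP change is adjusted for the ACE/ARB stratum but not for baseline SBP. A 1-SE imbalance then shifts each visit estimate by roughly 0.5-2.1 mmHg in the same direction, which is well inside the 3.1-5.9 mmHg standard error. The variance effect of adjusting runs from a 10% cut to a 2% loss at 20 versus 10. These sizes rest wholly on the assumed means and SDs, on 20 versus 10 being available at each visit, and on there being no adjusted analysis in the redacted text. The mechanism depends only on b being below 1. The same reasoning applies to DBP where protocol 10.6.3 compares it.

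**What to change.** In SAP 3.4, and in protocol 10.6.3 so that the two agree, specify ANCOVA for the SBP change comparisons with treatment, ACE/ARB stratum and baseline SBP. Do the same with baseline DBP where DBP is compared. Report the adjusted difference with its 95% CI at each visit. State that the residuals used for the normality check come from this model, and that a visit analysed by van Elteren is unadjusted. The primary AGT model and its fallback need no change.

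The cost is one covariate in the wording, no new data, and one residual degree of freedom. If a protocol amendment for this alone seems disproportionate, the SAP can carry the change and the protocol can be aligned at its next revision.
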